8.3.1. Recording of adverse events

It is the responsibility of the Investigator to ensure that an AE in a clinical trial is registered. At each visit (other than screening), the Investigator should record all observed subjective or objective AEs.

When a patient has an AE, the investigator should describe the AE in as much detail as

possible and record the AE in the CRF.

The Investigator should complete the relevant pages of the AE in the CRF, indicating the classification of the AE (seriousness, severity, IP relationship). The date and time (if applicable) of the occurrence and resolution of the AE, unexpected AE or previously described/known AE, possible association with investigational product administration, patient and drug interventions, drug therapy for the AE, and outcome/resolution of the AE should also be recorded in the CRF.

Any available information related to the recorded AE, such as results of diagnostic tests (laboratory tests, ECG, etc.) should also be reflected in the CRF.

Categories of actions taken

One of the following categories is used to record actions taken in relation to an AE:

- No action required (continuation of the trial according to the protocol).
- Reducing the dose, which could mean:
 - o reducing the dose of the investigational product;
 - o reducing the frequency of administration/intake.
- Cancellation of investigational product followed by resumption.
- Complete withdrawal of the investigational product (complete discontinuation of the investigational product).
- Prescribing other treatments, such as:
 - o for the treatment of an AE,
 - o changing the dosage of concomitant therapy, prescribing non-drug therapy.

8.3.2. SAE reporting

Requirements for reporting of SAEs by the Investigator

All SAEs should be traced back to their resolution or stabilization.

If a SAE develops, it should be recorded in the patient's source documentation and CRF and an NPT SAE Registration Form should be completed. The SAE form is completed and submitted to the Sponsor's APP/CRO representative within 24 hours of the Investigators' receipt of the SAE information.

Representative of a contract research organisation (CRO):

Name of the contract research organisation:	Limited Liability Company Klin PharmDevelopment
Responsible for receiving SAE reports:	Person responsible for pharmacovigilance in the CRO
e-mail:	[contact]

Authorized Person for Pharmacovigilance RPC PHARMASOFT LLC:

Name of the Sponsoring Company:	RPC PHARMASOFT LTD
Name of the person responsible for receiving reports on the development of SAE:	[name]
Phone:	[contact] [name]
e-mail:	[contact]

The Investigator must comply with the following deadlines for sending SAE communications to the Sponsor's APP/ CRO representative:

- Within 24 hours of being informed of the SAE onset.
- When new information on the SAE becomes available.
- After 30 days, if the SAE is still in progress.
- After the end of the SAE.

Each message should contain as much information as possible, including:

- Trial number (identifier or protocol number).

- Patient number.
- Investigator's full name and contact details.
- Description of the adverse event (date of onset, outcome as of the date of the report).
- Result of the investigator's assessment of the seriousness and severity.
- The result of the investigator's assessment of relationship with the investigational product.

The investigator should apply maximum effort to uncover new information on the course of the SAE.

Additional information (follow-up data) on all SNPs not available at the time of the initial report must be provided by the investigational site to the Sponsor's APP/CRO representative, within 24 hours of the Investigator becoming aware of this additional information.

The SAE form is completed, dated and signed by the Investigator who is authorized to complete the source documentation and the CRF.

Investigational site personnel should report SAEs to the local Ethics Committee in accordance with the rules and procedures established by the institutional board.

Responsibilities of the Sponsor

The sponsor is responsible for assessing the safety of the investigational product in the clinical trial.

The Sponsor is responsible for promptly informing the Investigator, the local ethics committee, and regulatory authorities of any findings that may adversely affect patient safety and the conduct of the trial.

The sponsor must submit information on all serious unexpected adverse reactions (hereinafter referred to as SUARs) for the investigational medicinal product identified during the clinical trial to the regulatory authorities:

- no later than 7 calendar days from the date of receipt of information on the identification of SUARs, if they have resulted in death or were life-threatening;
- no later than 15 calendar days from the date of receipt of information on the identification of SUARs for other serious unexpected adverse reactions.

Within 15 calendar days, the sponsor must submit to the regulatory authority and the Ethics Committee other safety information that may change the assessment of the risk/benefit ratio of the investigational medicinal product or serve as a basis for changes in the recommendations for its prescribing, as well as a basis for reconsideration of the possibility of further conduct of the trial.

The Sponsor may delegate to the contract research organisation its authority to communicate information about the SAE to regulatory authorities, ethics committees, and to the Investigator.

Duration of follow-up of patients after the development of AE

The investigator is responsible for documenting information about AEs during the clinical trial period.

In the event of a patient's death, the investigator shall provide the Sponsor's APP/CRO representative and the Ethics Committee with all necessary additional information.

If a patient develops an AE, the investigator should enter the necessary information into the CRF by completing the appropriate pages and assess whether the patient can continue to participate in the trial (continue the IP or exclude the patient from the trial). If a SAE develops, the investigator completes the SAE registration form provided by the Sponsor/contract research organisation representative, assesses whether it is associated with the investigational product and faxes the completed form to the Sponsor/contract research organisation representative. The original SAE form and fax receipt acknowledgement sheet should be retained in the source documentation, and the information should be entered into the patient's CRF. SAEs are reported to the LEC; SAEs deemed to be SUARs are reported to regulatory authorities, in accordance

with pharmacovigilance practices. The CRO/Sponsor representative has the right to urgently request additional information from the Investigator about such SAEs for reporting to the regulatory authorities.

In the context of reporting of SAEs, the trial period is defined as the period from the first administration of the investigational product to the end of the follow-up period.

During the trial period, the investigator is obligated to provide patients with necessary medical services.

If, prior to completion of the trial, patients develop an AE that results in exclusion from the trial, it is the responsibility of the investigator to ensure follow-up of that patient. Follow-up of the patient to ensure patient safety should take precedence over establishing the cause(s) for the development of the AE. The frequency of examinations during the follow-up period is determined by the investigator. All AEs/SAEs should be monitored until they are resolved or stabilized.

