4.4. Expected duration of patient participation in the trial

The total duration of patient participation in the trial will be no more than 74 days, including the screening period.

The trial will include the following periods and visits:

- **Screening** (Visit 0) - pre-screening of patients.

The duration of the period should not be more than 24 hours from the time of the informed consent procedure to randomization. Screening, randomization and initiation of therapy can be done on the same day.

- **Randomization and initiation of therapy** (Visit 1) - randomization of patients, initiation of trial therapy.

- **Therapy period** (Visits 2-4, Phone calls), use of investigational product/placebo (Duration of therapy - 70 days: 10 days - period of parenteral administration, 60 days - oral administration), assessment of the patient's condition, registration of AE. The total patient period, including scheduled procedures, is 71 (+2) days.

4.5. Suspension, termination of the trial, termination of participation in the trial by individual subjects

The sponsor has the right to temporarily suspend the trial at any time for reasons including, but not limited to, safety, ethical, or administrative issues.

The sponsor has the right to terminate the trial at any time if the goals and objectives of the trial are not being met.

In doing so, the Sponsor must notify the Investigator or the management of the investigational site of the temporary suspension or early termination of the trial in writing.

If the trial is suspended or terminated for safety reasons, the Sponsor will immediately inform the Investigator, as well as regulatory authorities and ethics committees.

The Investigator has the right to terminate participation in the trial (withdraw from the trial) of individual subjects when exclusion criteria are found.

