5.4. Termination of subjects' participation in the trial

5.4.1. Procedures for excluding subjects from the trial

Criteria for non-inclusion of patients in the trial (assessed at the screening stage) are presented in section 5.2.

The criteria for exclusion of patients from the trial (assessed throughout the trial in accordance with the description of the trial procedures and the Schedule of Trial Procedures (Appendix 1) are presented in Section 5.3.

If a patient decided to withdraw from the trial or did not complete the trial for any reason, his/her randomization code should not be reused.

Patients who were excluded from the trial during screening prior to the administration of investigational therapy should not be randomized into this trial.

Excluded subjects will be monitored for the development of AE/SAE until their resolution or stabilisation of AE/SAE-induced manifestations.

5.4.2. Data collection by type and timing for subjects who discontinued participation in the trial

The investigator transmits data on patients excluded from the trial to the Sponsor and the Clinical Research Associate within 24 hours in the form of a report that includes information about the patient's status at the end of the trial.

Patient status at the end of the trial:

1. Finished the trial.
2. Did not finish/discontinued because of:
 - trial error;
 - adverse events;
 - serious adverse events;
 - pregnancy;
 - protocol violations;
 - patient's desire to withdraw from the trial;
 - due to a patient's failure to appear;
 - other reasons (specify).

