8.3. AE recording and reporting

Adverse events (AEs)

The protocol provides for the recording of all AEs that occur to the patient after the first administration of the trial therapy and until the end of the patient's participation in the trial.

During screening, information about medical adverse events will be attributed to the patient's medical history (pre-existing/concomitant conditions).

The planned trial will record all deviations in the health status of patients (based on the results of physical examination, laboratory and instrumental methods of investigation) from the data obtained at the Screening and from the accepted reference values.

After obtaining the necessary information, the investigating physician will categorise the patient's condition as 'normal', 'clinically insignificant abnormalities' or 'clinically significant abnormalities'. In case the abnormalities detected during the trial have not been previously reported, or there is an aggravation of the patient's condition vs. the data obtained at Screening, the detected abnormalities will be classified as AEs.

If the abnormalities detected during the trial have been recorded at Screening and there is no significant negative trend in the reasonable opinion of the investigator, the detected abnormalities will be classified as clinically insignificant abnormalities (CIA).

All detected abnormalities, irrespective of whether they are attributed to AE or CIA, will be analysed when reporting the results of the clinical trial.

An adverse event is defined as any adverse change in the health status of a patient or subject of a clinical trial/trial to whom a medicinal product has been administered, irrespective of the causal relationship with its use.

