Patient group	Group	$\mu \pm SD$	Efficacy evaluation:	
			95% CI for the difference in mean ($\mu_{\text{Mex.}} - \mu_p$)	Comparison between groups
ITT population (n = 144)	Group I (Mexidol®, n = 72)	2.278 ± 0.755	DM = 0.292 (0.027; 0.556)	p = 0.029 (Mann-Whitney U-test)
	Group II (Placebo, n = 72)	1.986 ± 0.847		

According to the results of the EPICA clinical trial, the mean value of the change in the mRS score at the end of the course of therapy relative to the baseline level in the group of therapy with the investigational product was (mean (SD)) 2.278 (0.755) points, in the placebo group - 1.986 (0.847) points 2.278 (0.755) points, in the group of placebo therapy - 1.986 (0.847) points, the difference (Mexidol® - placebo) is 0.292 points, 95% confidence interval for the difference (Mexidol® - placebo) is (0.027, 0.556). The "superiority" boundary (δ) was chosen as the lower boundary of the confidence interval constructed for the difference (Mexidol® - placebo). Thus, $\delta = 0.027$ points.

To test the hypothesis of "superiority" of therapy with the investigational product compared with placebo therapy **at a significance level of $\alpha = 0.05$ (5%) to ensure power $1-\beta = 0.8$ (80%)**, the sample size was calculated for the primary efficacy criterion given the parallel design, a 1:1 randomization scheme (i.e., $k = 1$ - the ratio of sample sizes of the groups n_T/n_p), the expected difference in efficacy between the compared products $\varepsilon = 0.292$ and with a mixed standard deviation (SD) of the in-group efficacy $\sigma = 0.802$ points.

The formula [Chow Sh.-Ch., Shao J., Wang H., 2008] was used in the calculation:

$$n_T = n_R \frac{\frac{(1 + 1/k) * (z_\alpha + z_\beta)^2 * \sigma^2}{(\varepsilon - \delta)^2}}{\frac{2 * (1.6449 + 0.8416)^2 * 0.802^2}{(0.292 - 0.027)^2}} \approx 114 \text{ people/gr,}$$

where z_α and z_β - quantiles of the normal distribution $N(0,1)$ (mean: 0, standard deviation: 1).

The minimum number of patients completing the trial in accordance with the protocol must be at least $N = 2 * 114 = 228$ patients (114 patients per group).

Given the possible attrition of patients in the trial, it is planned to **randomize 304 patients**, of whom **at least 228 should complete the trial according to the Protocol**.

Given the potential dropout of patients during the Screening phase, approval is planned for a clinical trial with a total of **336 screened patients**.

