Safety assessment will be carried out based on the analysis of the frequency of occurrence of all adverse events, dynamics of laboratory and instrumental parameters.

AEs are recorded after the first use of the drug until the patient completes the trial and are tracked throughout the trial until they are resolved/stabilised.

Frequency tables with data on discontinuation of therapy or changes in therapy parameters due to AEs will be presented.

Pre- and post-trial data will be compared to assess safety parameters.

All data will be analyzed on the safety population. Regardless of the reason for trial termination, data from all included patients will be included in the safety analyses of the trial therapy.

Adverse event (AE) is any adverse change in the health status of a patient or subject of a clinical trial to whom a medicinal (investigational) product has been administered, regardless of the causal relationship with its use.

Serious adverse event (SAE) - any adverse medical event that, regardless of the dose of the medicinal product, has resulted in death, is life threatening, requires hospitalization or its prolongation, has resulted in permanent or significant disability or impairment, is a congenital anomaly or birth defect or other medically significant event.

Adverse reaction (AR) - unintentional adverse body reaction associated with the use of a medicinal product/investigational product, suggesting at least a possible relationship with the use of a suspected medicinal product/investigational product.

Unexpected adverse reaction (UAE) - an adverse reaction, the nature, severity or outcome of which does not correspond to the information in the current instructions for medical use of the medicinal product or in the investigator's leaflet for an unregistered medicinal product.

Serious unexpected adverse reaction (SUAR) - an unexpected adverse reaction that is characterized by features of a SAE.

The parameters of the AE/SAE will be estimated as follows:

Severity of AEs:

The investigator assesses the severity of an adverse event according to the Common Terminology Criteria for Adverse Events (CTCAE) current version at the time of the trial. If an adverse event cannot be classified according to the CTCAE criteria, the Investigator will select the closest description of the severity of the adverse event from those given in the classification based on personal clinical experience:

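### The AE and SAE collection windows do not agree, so new deaths and SAEs after exclusion are not reliably collected to a common time point

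*Protocol*

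**What the plan says.** Several sections set the safety window, and they set it differently.

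- Protocol 8.3 records AEs "after the first administration of the trial therapy and until the end of the patient's participation in the trial".
- SAP section 10 states that "AEs are recorded after the first use of the drug until the patient completes the trial", and adds that recorded events are tracked until resolved or stabilised.
- Protocol 13.4 has the eCRF of an early dropout filled in only as far as the dropout.
- Protocol 8.3.2, for SAE reporting: "the trial period is defined as the period from the first administration of the investigational product to the end of the follow-up period".
- Protocol 5.4.1: "Excluded subjects will be monitored for the development of AE/SAE until their resolution or stabilisation of AE/SAE-induced manifestations".
- Protocol 5.4.4 follows patients excluded for an AE or SAE until it resolves or stabilises. For other exclusions after dosing it asks only for an end-of-trial visit.

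The design has three periods: screening, randomization with start of therapy, and therapy. Section 4.4 states: "The total patient period, including scheduled procedures, is 71 (+2) days", and "The total duration of patient participation in the trial will be no more than 74 days, including the screening period". The only other mention of a follow-up period in 8.3.2 concerns patients excluded because of an AE: "The frequency of examinations during the follow-up period is determined by the investigator". No end date is given.

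Section 5.3 excludes patients for, among other things, recurrent stroke, AEs or SAEs that make continuing dangerous, need for non-permitted therapy, loss of contact, and a positive SARS-CoV-2 test. Section 9.7.3 compares the number of patients with AEs by Fisher's exact or Pearson's test in the ITT population, and SAP Table 20 adds a relative risk. Neither uses time at risk.

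**The concern.** A crude proportion of patients with an event estimates a 71-day risk only if everyone is observed for 71 days. Here some patients leave observation early, partly because of how they are doing, and the plan does not say clearly what is collected afterwards. One site could go on asking about new events under 5.4.1; another could close the record under 8.3 and 13.4.

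Take a patient excluded for recurrent stroke on day 15 whose condition is stable by day 25 and who dies of pneumonia on day 40. The death comes after participation has ended and after the excluding event has stabilised, so no section clearly requires it to be found and recorded. At stake are complete 71-day death and SAE risks by arm and, if exclusion differs between arms, the direction of the safety comparison.

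**Working it through.** **1. The windows side by side.** Sections 8.3 and 13.4 and SAP 10 end recording at participation, dropout or completion. Sections 5.4.1 and 5.4.4 extend it to resolution or stabilisation. Section 8.3.2 extends it to an undefined point. No section sets a common calendar date or a vital-status check after exclusion.

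**2. How many patients could be affected.** The plan's sample size reproduces: 2 × (1.6449 + 0.8416)² × 0.802² / (0.292 − 0.027)² = 113.3, so 114 per group and 228 in total. The allowance introduced with "Given the possible attrition of patients in the trial" is (304 − 228)/304 = 25%, or 76 patients. These are patients not completing per protocol, so 76 early leavers is an upper bound. In EPICA (protocol 2.3.2), 9 of 150 dropped out early: 6%, or about 18 of 304.

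**3. Observation time lost.** Share lost = fraction excluded × (71 − day of exclusion)/71. Exclusion on day 11 or day 55 is an assumption.

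| Fraction excluded | Day 11 | Day 55 |
|---|---|---|
| 25% | 0.25 × 60/71 = 21.1% | 0.25 × 16/71 = 5.6% |
| 6% | 0.06 × 60/71 = 5.1% | 0.06 × 16/71 = 1.4% |

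**4. Effect on the comparison.** Assume the same constant hazard in both arms, a 71-day risk p of 10%, all exclusions on day t, and no new event recorded afterwards. Observed risk = (1 − d) × p + d × q, where d is the fraction excluded and q = 1 − (1 − p)^(t/71), which is 0.0162 at day 11 and 0.0576 at day 40.

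| Excluded, arm 1 vs arm 2 | Day 11: risks, ratio (arm 2 / arm 1) | Day 40: risks, ratio (arm 2 / arm 1) |
|---|---|---|
| 25% vs 25% | 0.0790 and 0.0790, 1.00 | 0.0894 and 0.0894, 1.00 |
| 20% vs 30% | 0.0832 and 0.0749, 0.90 | 0.0915 and 0.0873, 0.95 |
| 15% vs 35% | 0.0874 and 0.0707, 0.81 | 0.0936 and 0.0852, 0.91 |

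With p = 5% the ratios are the same to two decimals. The arm with more exclusions looks safer.

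**5. Deaths missed.** The documents give no mortality rate for this trial; 5% to 10% by day 71 is an assumption. Assume exclusions spread evenly over 71 days and a hazard after exclusion equal to, or three times, that of other patients (hazard ratio h). With a = −h × ln(1 − p), the expected fraction of excluded patients dying between exclusion and day 71 is 1 − (1 − e^(−a))/a.

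| Mortality, h | Fraction | 18 excluded | 76 excluded |
|---|---|---|---|
| 5%, 1 | 0.0252 | 0.5 | 1.9 |
| 5%, 3 | 0.0731 | 1.3 | 5.6 |
| 10%, 1 | 0.0509 | 0.9 | 3.9 |
| 10%, 3 | 0.1426 | 2.6 | 10.8 |

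EPICA reported no deaths. The one-sided 95% upper bound for 0 of 150 is 1 − 0.05^(1/150) = 2.0%. At 2% mortality the range falls to 0.2 to 0.5 deaths with 18 excluded and 0.8 to 2.3 with 76.

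**The case against.** The protocol provides more safety follow-up than the window definitions alone suggest. Section 5.4.1 covers all excluded subjects whatever the reason, and its wording can be read to include new events. Section 5.4.4 follows AE-related exclusions to resolution or stabilisation, 8.3.2 requires the same for every SAE, investigators must supply information on a death, and unscheduled visits or calls are allowed. The follow-up period in 8.3.2 may simply mean the time after exclusion for an AE.

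Most of this stands, and it rules out four stronger readings that a reader might infer.

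- *Later deaths and SAEs are not captured at all.* Not supported: an event open at exclusion, and a death resulting from it, is to be followed and reported.
- *The sickest patients have the shortest windows.* Not supported in general: AE-related exclusions get open-ended follow-up, and the single closing visit is for the others. Even a positive SARS-CoV-2 test might count as an AE, because 8.3 classes newly found abnormalities that way. The point applies only to new events once the excluding event has stabilised.
- *The arms will be compared over unequal windows.* Not shown: nothing in the documents predicts different exclusion rates or timing.
- *The loss equals the whole safety signal.* This needs all 76 patients to leave early and an assumed mortality. It also counts deaths from the excluding event, which the plan does follow.

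The inconsistency remains. On the generous reading, 5.4.1 still has no end date or contact schedule, and it disagrees with 8.3 and 13.4. The duty to report on a death does not ensure that the site hears of it.

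**Conclusion.** The concern holds in a limited form. The windows are inconsistent and the follow-up period is undefined, so new-onset SAEs and deaths after exclusion are not reliably collected to a common time point. This leaves 71-day risks by arm incomplete whether or not exclusion is balanced. Bias between arms is conditional on a difference in exclusion rate or timing.

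The likely loss is small in absolute terms: about 0.5 to 2.6 deaths if dropout resembles EPICA's, with an upper bound of about 2 to 11, and fewer if mortality is lower. These figures rest on assumed mortality, an assumed hazard ratio, even timing of exclusions, and the assumption that no death after exclusion is recorded. EPICA enrolled NIHSS 5 to 20 rather than 9 to 15, so its dropout and absence of deaths are only a guide. When few events are expected, each omission counts, and the remedy is cheap. The plan should be changed, but this is not a fatal flaw.

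**What to change.** Reconcile protocol sections 5.4.1, 5.4.4, 8.3, 8.3.2 and 13.4 with SAP section 10 by defining one window: AEs, SAEs and vital status are collected for every dosed patient from first dose to day 71 (+2), whether or not treatment or visits stopped, unless consent to contact is withdrawn. Replace the undefined end point in 8.3.2 with this date, and keep the existing follow-up of open events to resolution or stabilisation.

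For excluded patients, keep the scheduled calls on days 24 and 55 and add one day-71 call to the patient or a relative. Report deaths and SAEs by arm over this common window, preferably with a time-to-event or exposure-adjusted summary beside the crude counts.

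The cost is protocol, SAP and consent wording and up to three short calls per excluded patient: at most 76 × 3 = 228 calls, or about 18 × 3 = 54 at EPICA's dropout. No visits or tests are added, and the sample size stays at 114 per group and 304 randomized.
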